3 STUDY DESIGN

This is a prospective, pilot study to investigate the presence or absence of antibiotic resistant organisms after treatment of chronic rhinosinusitis with topical antibiotics. In addition, therapeutic effects of the topical antibiotics will be investigated via assessment of patient symptoms, and physical exam endoscopic findings.

There will be 1 study group with 20 patients.

The patients will first undergo pre-intervention assessment in the outpatient setting. This will occur in the Department of Otorhinolaryngology on the 12th floor of the Gonda building in Rochester, MN with one of the staff rhinologists. Patients will be selected to participate if they have active mucopurulence on their endoscopic examination. The assessment will consist of 1) obtaining a nasal swab of mucopurulence from the affected sinus to be sent for gram stain, culture and sensitivity, 2) assessment of patient symptom severity score as measured by the self-administered Sino-Nasal Outcomes Test (SNOT-22) survey, and 3) assessment of patient physical exam as evaluated by rigid nasal endoscopy and documented in Lund-Kennedy endoscopic findings form.

The study intervention is the administration of culture directed topical antibiotics over 28 days. These antibiotics will prescribed to the patient in capsule form as compounded by the Mayo Clinic pharmacy, or suitable licensed compounding pharmacy. One capsule will subsequently be added to a nasal saline irrigation bottle, and the patient will administer this irrigation to him or herself in the usual fashion twice per day.

- The dosages of the antibiotic capsules were determined by the Mayo Clinic pharmacy team with input from infectious disease, based upon available published data, and will be as follows, dissolved in a standard 240mL saline irrigation rinse
 - Mupirocin: 30 mg
 - Tobramycin: 192 mg
 - Gentamicin: 192 mg
 - Levofloxacin: 250mg

After the completion of the study intervention (within 21 days), the patient will undergo post-intervention assessment in the outpatient setting, again in the Department of Otorhinolaryngology with one of the staff rhinologists. The patient will again be assessed with 1) nasal swab from the affected sinus sent for gram stain, culture and sensitivity 2) SNOT-22 symptom scores and 3) Lund-Kennedy endoscopic exam scores.

SELECTION AND ENROLLMENT OF PARTICIPANTS 4

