Topical Antibiotics in Chronic Rhinosinusitis

NCT03673956

August 26, 2018

Topical Antibiotics in Chronic Rhinosinusitis

v3 8-26-18

i

PRÉCIS

Study Title

Topical Antibiotics in Chronic Rhinosinusitis

Objective

The primary objective is to show that the use of topical antibiotics in the treatment of chronic rhinosinusitis does not lead to antibiotic resistant organisms. The secondary objectives are to investigate the effects of topical antibiotics on patient symptoms as measured by the validated Sino-Nasal Outcomes Test (SNOT-22) and physical exam endoscopic findings as documented by Lund-Kennedy endoscopic scoring system.

Design and Outcomes

This is a prospective pilot study to evaluate development of antibiotic resistance in patients with chronic rhinosinusitis who are being treated with topical antibiotics.

Interventions and Duration

Intervention includes 28 days of culture directed antibiotic therapy with one of the following four topical antibiotics: Tobramycin, Mupirocin, Gentamicin or Levofloxacin

Sample Size and Population

There will be 20 participants total in the study and they will all receive the intervention.

STUDY TEAM ROSTER

Principal Investigator: [name]

[name], MD

[contact] [contact]

Co-Investigators:

[name] [contact]

[name] [contact]

Study Team:

[name] [contact]

[name], MS Biostatistician Phone:

[name], CCRP Research Coordinator

[name] Research Coordinator

Phone: Pager:

1 STUDY OBJECTIVES

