Our department has developed in conjunction with the infectious disease department and the Mayo pharmacy, an easy to implement set of topical antibiotics with easy to use capsules and set dosages for use by our patients. This is a pilot study designed with the hypothesis that topical antibiotics do not cause antibiotic resistance. In addition, data will be collected to investigate symptom and physical exam outcomes in patients undergoing topical antibiotic therapy as secondary outcomes. The study will be conducted on existing patients who would otherwise receive treatment with topical antibiotics as standard of care.

Moreover, many of patients who have recalcitrant chronic rhinosinusitis are infected by the bacteria pseudomonas aeruginosa. The use of the fluoroquinolone class of antibiotics is a treatment of choice for this pathogen. In 2008, the US Food and Drug Administration issued a "black box" advising manufacturers to warn providers and patients of risk increased risk of tendinitis, tendon rupture, peripheral neuropathy. A well-studied, viable alternative to oral fluoroquinolone that works well without the associated risks is warranted.

Finally, poor penetration of oral antibiotics to the sinonasal cavity due to the infection being within a space may limit the efficacy of oral antibiotics as a treatment. In contrast use of topical antibiotics in a patient who has previously undergone sinus surgery, provides a potentially more effective delivery of medication to the infected space⁸.

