2.2 Study Rationale

The interventional regimen is as follows.

Patient will undergo pre-intervention nasal swab from the affected sinus that will be sent for gram stain and bacterial culture and sensitivities.

If pathogen identified in the bacterial culture is pseudomonas aeruginosa, topical tobramycin or gentamycin will be assigned as first line agent pending culture profiles and cost factors. If the sensitivities show resistance to both tobramycin and gentamycin, then levofloxacin will be prescribed.

If the pathogen identified in the bacterial culture is other than pseudomonas aeruginosa, mupirocin will be prescribed. If the pathogen shows resistance to mupirocin, then the patient will be prescribed one of the other three antibiotics will be prescribed pending culture profiles and cost factors

The patient will use the topical antibiotic twice a day for 28 days. This will be accomplished by first proceeding with their normal nasal rinse regimen as prescribed by their physician (this may include saline alone, or saline with budesonide). Twice per day, at the end of each regimen, they perform one additional nasal saline rinse using the Neil Med sinus rinse bottle in the manner outlined on the packaging instructions. However, with this last additional nasal saline rinse, they will open their antibiotic capsule and drop the contents into the rinse bottle prior to rinsing.

Known and potential risks are as follows:

Potential risks of nasal saline irrigation is stinging sensation and burning Potential risks of filling the nasal saline irrigation rinse bottle with water that is too hot is mucosal burns

Potential risks of topical antibiotic administration include local pruritis and inflammation Potential risks of selection antibiotic resistant organisms. Potential risk for hearing loss

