9.4 Outcomes

9.4.1 Primary Outcome

Post treatment assessment of presence of antibiotic resistant organism as assessed by nasal swab sent for gram stain, culture and sensitivity

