9.5 Data Analyses

Statistical Methods

Continuous patient characters will be summarized with means and standard deviations for features that are approximately normally distributed and with medians, interquartile ranges, and ranges otherwise. Categorical features will be summarized with frequency counts and percentages.

Primary endpoint:

Number and proportion of patients who developed antibiotic resistance organism will be summarized. 95% confidence intervals will be provided for the proportion.

Secondary endpoint:

1) SNOT-22 symptom scores and Lund-Kennedy endoscopic exam score will be summarized as mean (standard deviation) and median (range).

2). Definition of adherence to study intervention will be to complete 25 of 28 days of topical antibiotics and attend the pre-intervention / enrollment visit as well as the post-intervention assessment visit. Number and proportion of patients with adherence will be reported.

3) Audiometric data will be summarized as a mean (standard deviation) and median (range)

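### The primary result is a yes/no count of patients with a resistant organism, with no rule for intermediate results and no paired comparison with the baseline sensitivities

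*Combined protocol and SAP*

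**What the plan says.** The primary result has two outcomes per patient wherever it appears. Section 3 aims to "investigate the presence or absence of antibiotic resistant organisms after treatment of chronic rhinosinusitis with topical antibiotics". Section 9.4.1 defines the outcome as "Post treatment assessment of presence of antibiotic resistant organism as assessed by nasal swab sent for gram stain, culture and sensitivity". Section 9.5 gives the analysis: "Number and proportion of patients who developed antibiotic resistance organism will be summarized", and "95% confidence intervals will be provided for the proportion".

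The laboratory data are richer than that. Section 2.2 states: "Patient will undergo pre-intervention nasal swab from the affected sinus that will be sent for gram stain and bacterial culture and sensitivities". Section 3 repeats the procedure after treatment: "nasal swab from the affected sinus sent for gram stain, culture and sensitivity 2) SNOT-22 symptom scores". Sections 5.2 and 6.1 say the same.

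The documents do not define resistant. They name no breakpoint standard, do not say which drugs count, give no rule for an intermediate result and do not match species before and after. Sections 9.4.2 and 9.5 contain no graded or paired susceptibility summary, even as a secondary outcome.

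On purpose, section 2.1 says: "This is a pilot study designed with the hypothesis that topical antibiotics do not cause antibiotic resistance". The précis goes further: "The primary objective is to show that the use of topical antibiotics in the treatment of chronic rhinosinusitis does not lead to antibiotic resistant organisms". Section 1.1 aims only to describe the results.

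**The concern.** Two gaps sit in the same definition.

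The first is the scale. If only an isolate reported as resistant is an event, a patient whose isolate was susceptible before the course and intermediate after it is reported as having developed nothing. The loss of susceptibility is on file in the two reports but does not reach the result. Because no rule is written, the class given to intermediate results could also be chosen after the results are seen.

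The second is the reference point. Section 9.4.1 scores what is present after treatment. Section 9.5 counts patients in whom resistance developed, which requires a comparison with baseline that is nowhere specified. A patient who carried a resistant organism throughout is an event under one section and not under the other.

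At stake is what the trial can say about resistance. A headline of no resistant organisms would be read as support for the hypothesis in section 2.1, and it could stand beside several paired isolates that lost susceptibility.

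**Working it through.** **Inputs**

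- Scale of the primary result: yes/no per patient (sections 3, 9.4.1, 9.5).
- Number of patients: 20 in the précis and section 3, 40 in sections 9.1 and 9.2. The two need reconciling; both are shown.
- Interval: 95%, method not named (section 9.5). The exact (Clopper-Pearson) interval is assumed.
- Patients with a step down that does not reach resistant, *k*: the documents give no figure. Assumed at 5%, 10% and 20% of patients.
- Patients with resistance at baseline that persists, *b*: no figure given. Assumed at 1 for illustration.
- Every patient is assumed to have a paired isolate. With fewer pairs the intervals for the paired count widen.

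The plan states no power, margin or derived sample size, so there is no figure to reproduce.

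**Step 1: what each reading counts**

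| Before to after, same species | Only resistant counts | Intermediate grouped with resistant | Any step down |
|---|---|---|---|
| Susceptible to intermediate | not counted | counted, but not told apart from susceptible to resistant | counted |
| Susceptible to resistant | counted | counted | counted |
| Intermediate to resistant | counted | not counted as new | counted |
| Resistant to resistant | counted under 9.4.1, not under 9.5 | counted under 9.4.1, not under 9.5 | not counted |

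Either way of classing intermediate loses something; only the shift table keeps all the rows apart.

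**Step 2: size of the difference**

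For *x* events in *n* patients, the lower limit is the 0.025 quantile of Beta(*x*, *n* − *x* + 1) and the upper limit is the 0.975 quantile of Beta(*x* + 1, *n* − *x*). For *x* = 0 the upper limit is 1 − 0.025^(1/*n*):

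- *n* = 20: 1 − 0.832 = 0.168
- *n* = 40: 1 − 0.912 = 0.088

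With no isolate reaching resistant:

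| N | *k* (assumed) | Only resistant counts (95% CI) | Any step down (95% CI) |
|---|---|---|---|
| 20 | 1 | 0% (0 to 16.8%) | 5% (0.1 to 24.9%) |
| 20 | 2 | 0% (0 to 16.8%) | 10% (1.2 to 31.7%) |
| 20 | 4 | 0% (0 to 16.8%) | 20% (5.7 to 43.7%) |
| 40 | 2 | 0% (0 to 8.8%) | 5% (0.6 to 16.9%) |
| 40 | 4 | 0% (0 to 8.8%) | 10% (2.8 to 23.7%) |
| 40 | 8 | 0% (0 to 8.8%) | 20% (9.1 to 35.7%) |

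**Step 3: direction**

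Let *r* patients become resistant. The literal rule gives *r*/*n*. Adding the *k* step-downs gives (*r* + *k*)/*n*, which is never smaller. On the literal rule, then, the omission can only lower the count.

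The reference point works the other way. If *b* patients carry resistance from baseline, 9.4.1 gives (*r* + *b*)/*n* and 9.5 gives *r*/*n*. With *r* = 0, *b* = 1 and *n* = 20, that is 5% (0.1 to 24.9%) under 9.4.1 and 0% (0 to 16.8%) under 9.5.

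**The case against.** The strongest reply is that this is a descriptive pilot. Sections 1.1 and 9.2 say the aim is to describe results and to collect data for a larger study; no test, margin or success threshold rests on the proportion. A yes/no summary is then a less sensitive summary, not a mistake. That stands, and it limits the weight of the point. It does not remove it: the précis aims to show absence of resistance, and a study meant to inform a larger one is better served by the distribution of shifts than by one proportion.

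Some stronger readings are tempting, and the documents do not support them:

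- A reader might infer that the plan scores a move to intermediate as no change. It contains no rule for intermediate results, so this holds only if resistant is read literally.
- A reader might infer that the endpoint as a whole leans toward the hypothesis. Section 2.2 provides for patients whose isolate is already resistant to one or more of the study drugs, and 9.4.1 could count that carriage as an event, which pushes against the hypothesis. The direction is settled only for the step-down omission.
- A reader might assume that MICs are on the reports. The documents mention only culture and sensitivities.
- A reader might suppose that a partial loss of susceptibility is the likelier signal after 28 days, or put a figure on the share of losses missed. The documents give no rates, so any such share would only restate what was assumed.
- A reader might set susceptibility against drug concentration in the rinse. No planned analysis does so, and the point does not need it.
- A reader might infer that only a yes/no item is recorded. Section 10.1 does not say what the case report form captures.

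**Conclusion.** The point holds in a limited form. The primary result is a yes/no count resting on an undefined term, with two sections that disagree on whether baseline resistance is included, and the paired sensitivities already collected are not used in any planned comparison.

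On the literal reading, step-downs to intermediate are lost and the loss can only favour the no-resistance hypothesis. Its size depends on a rate the documents do not give. At an assumed 4 of 20 patients it is the difference between 0% and 20%; at 1 of 20 it is the difference between 0% and 5%, with widely overlapping intervals. These figures assume exact intervals, no isolate reaching resistant and a paired isolate in every patient.

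This is a worthwhile, inexpensive improvement to the definition and reporting of the primary result. It does not invalidate the design.

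**What to change.** Settle the following before any post-treatment results are reviewed.

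1. Keep the planned proportion, but state in both 9.4.1 and 9.5 that it counts patients with an organism that is resistant after treatment and was not resistant at baseline. State how an intermediate result is classed.
2. Add to 9.5, for the assigned antibiotic and from the same reports, a paired same-species table of susceptible, intermediate and resistant, before versus after. Report the number and proportion of patients with any step down, with an exact 95% CI, and give the number of patients with paired isolates as the denominator.
3. List paired MICs only where the laboratory reports them.
4. Word the conclusion on resistance from both counts. Neither replaces the other: the paired table cannot show a resistant species that was absent at baseline, and the planned proportion, if intermediate is not classed as resistant, cannot show a step to intermediate.

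The cost is SAP wording and transcribing the reported category for each isolate. No extra swab, visit or laboratory test is needed. The downside is a possibly less favourable headline if intermediate isolates appear.

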1.1 Primary Objective

The primary objective is to describe the results of antibiotic resistant organisms after the use of topical antibiotics in the treatment of chronic rhinosinusitis.

The secondary objectives are to investigate 1) the effects of topical antibiotics on patient symptoms as measured by the validated Sino-Nasal Outcomes Test (SNOT-22) and physical exam endoscopic findings as documented by Lund-Kennedy endoscopic scoring system. 2) the adherence to study intervention

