5.4 Adherence Assessment

Definition of adherence to study intervention will study subject attestation that they completed at least 48 / 56 dosages of nasal saline irrigation with topical antibiotic and presentation for one post-intervention assessment. Patient will record topical antibiotic use in a daily log. This log will be used by the investigators to assess adherence. These available endpoints will be taken and incorporated into analysis.

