8 INTERVENTION DISCONTINUATION

Participants may withdraw voluntarily from participation in the study at any time and for any reason. Participants should continue to be followed, with their permission, after study intervention has been administered.

Replacement of participants who discontinue early is allowed. The participants who are replaced will not be counted in the study and replacement can occur if participants do not complete the at least 48 / 56 dosages of intervention with topical antibiotics.

It is vital to collect safety data on any subject discontinued due to an AE or SAE. In any case, every effort will be made to undertake protocol-specified safety follow-up procedures. If voluntary withdrawal occurs, the subject will be asked to continue scheduled evaluations, complete an end-of-study evaluation, and be given appropriate care under medical supervision until the symptoms of any AE resolve or the subject's condition becomes stable.

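### Adherence is a stated objective and can decide who is counted, but doses taken are known only from the patient's own report, and no count of the capsules is planned as a cross-check

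*Combined protocol and SAP*

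**What the plan says.** Section 1.1 lists "the adherence to study intervention" as the second of the secondary objectives. Section 2.2 sets the regimen: "The patient will use the topical antibiotic twice a day for 28 days". Section 3 sets the unit of dose: "One capsule will subsequently be added to a nasal saline irrigation bottle, and the patient will administer this irrigation to him or herself".

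Section 5.4 defines adherence as "study subject attestation that they completed at least 48 / 56 dosages of nasal saline irrigation with topical antibiotic", together with attendance at one post-intervention assessment. The data source is also given there: "Patient will record topical antibiotic use in a daily log. This log will be used by the investigators to assess adherence".

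Section 8 uses the same threshold for a second purpose: "replacement can occur if participants do not complete the at least 48 / 56 dosages of intervention with topical antibiotics". It adds: "The participants who are replaced will not be counted in the study".

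Section 9.5 reports adherence as a count and a percentage but defines it differently, as 25 of 28 days of treatment plus attendance at both visits.

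Sections 5.2 and 6.1 list what happens at the post-intervention visit: swab, SNOT-22 and endoscopic scoring, with photographs in 6.1. Neither they nor any other section provides for returning capsules, counting them, or reconciling them with what was dispensed.

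**The concern.** Of the components of adherence, only visit attendance is observed by the study team. Whether the doses were taken comes from the patient, first as an attestation and then as a diary the patient keeps. If the two agree, that is one source agreeing with itself.

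Two things depend on it. The first is the adherence percentage, which is a planned result of a pilot whose stated purpose (section 9.2) includes gathering data for a larger study. The second is membership of the counted set. A patient who candidly reports 45 doses can be replaced and dropped, while one who took 45 and reports 50 stays in and is treated as having completed the course. The threshold therefore also affects the denominator of the resistance proportion.

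An independent check is available at a visit that already takes place, and the plan does not use it.

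**Working it through.** **Reproducing the plan's figure.** 2 doses a day (section 2.2) x 28 days = 56 doses, which matches the denominator in section 5.4. At one capsule per rinse (section 3), this is 56 capsules. The threshold is 48/56 = 85.7%, so at most 56 - 48 = 8 capsules may be left.

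**Size of undetected over-reporting, before any replacement.** The documents give neither a true adherence rate nor a misreporting rate, so both inputs are assumptions. Let A be the true share reaching 48/56, and m the share of patients below it who report reaching it.

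- Reported adherence = A + (1 - A)m
- Misclassified patients among n enrolled = n(1 - A)m

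Sections 3 and 9.2 give different sample sizes (20 and 40), so both are shown.

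| A | m | Reported | Misclassified of 20 | Misclassified of 40 |
|---|---|---|---|---|
| 60% | 25% | 70% | 2 | 4 |
| 60% | 50% | 80% | 4 | 8 |
| 80% | 25% | 85% | 1 | 2 |
| 80% | 50% | 90% | 2 | 4 |
| any | 0% | equal to A | 0 | 0 |

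**Effect of the replacement rule.** Suppose every patient who reports fewer than 48 doses is replaced and not counted. Reported adherence on the 48/56 rule is then 100% by construction: 20/20 (exact 95% CI 83.2% to 100%) or 40/40 (91.2% to 100%). This would happen with perfectly honest reporting, and equally if the rule were applied to a capsule count. The share of the retained set that is truly below threshold becomes (1 - A)m / [A + (1 - A)m]:

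- A = 60%, m = 25%: 0.10/0.70 = 14.3%, about 3 of 20
- A = 60%, m = 50%: 0.20/0.80 = 25%, 5 of 20
- A = 80%, m = 25%: 0.05/0.85 = 5.9%, about 1 of 20
- A = 80%, m = 50%: 0.10/0.90 = 11.1%, about 2 of 20

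**The two definitions.** 25/28 = 89.3%, against 85.7% for 48/56. If a day counts only when both doses are taken, 25 days need at least 50 doses. A patient with 48 or 49 doses then meets sections 5.4 and 8 but cannot meet section 9.5. The plan does not say how a day with one dose counts. A capsule total cannot settle the day-based version: 50 capsules used could be 25 full days, or 22 full days plus 6 days with one dose (22 x 2 + 6 = 50). Only a dated log can tell these apart.

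**The case against.** The strongest reply is that this is a design choice, not an error. Section 5.4 specifies a threshold, an attestation, a daily log reviewed by the investigators, and an observed visit. The study is a descriptive pilot in patients who would receive the treatment anyway. A daily log limits recall error, and nothing in the documents shows that it would be filled in late. All of this stands. It does not supply a second source for a stated objective, and the check costs little.

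A reader might also infer more than the documents support:

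- **That adherence will be overstated, by a known amount.** No misreporting rate or direction is given. Upward error is plausible, but the table rests wholly on assumed inputs.
- **That misreported doses feed the subtherapeutic-dosing worry in section 2.1 and so distort the primary result in a known way.** That section attributes the worry to a lack of standard dosing, not to missed doses, and the plan answers it with fixed capsule strengths.
- **That a capsule count should replace the log.** Lost, discarded or late-used capsules would count as taken. The visit may fall up to 21 days after treatment ends, so a count then cannot date the doses. It is a cross-check only.
- **That a capsule count alone would repair the adherence percentage.** It would not, because excluding replaced patients inflates the figure under either measure. Replacement is permitted rather than required, so 100% is the limiting case and not a certainty.

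**Conclusion.** The point holds as a cheap improvement. Dose-taking supports a secondary objective and can decide who is counted, it rests on self-report alone, and an available cross-check is not planned. Over-reporting could therefore not be detected.

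Its size is unknown. It is zero if nobody misreports. Under assumed true adherence of 60-80% and 25-50% misreporting among the non-adherent, it is about 1 to 4 of 20 patients (2 to 8 of 40) before any replacement.

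Two linked matters have to be settled for the reported percentage to mean anything: the exclusion of replaced patients from its denominator, and the conflict between the dose-based and day-based definitions.

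**What to change.** 1. **Sections 5.4 and 6.1:** record the number of capsules dispensed, ask the patient to bring the container to the post-intervention visit, and record the number left. List collection of the daily log in 6.1 as well.
2. **Section 9.5:** report adherence by capsule count (dispensed minus left) beside adherence by log, and show how many patients the two classify differently. Where the container is not returned, use the log alone and say for how many patients this was done.
3. **Sections 8 and 9.5:** report both figures over all enrolled patients, including any who are replaced, and state how many were replaced.
4. **Sections 5.4, 8 and 9.5:** reconcile the 48-of-56-dose and 25-of-28-day definitions. If a day-based definition is kept anywhere, state how a day with one dose counts and take it from the log.

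**Cost:** two case report form fields, a reminder to the patient, and one extra row or column in the adherence table. Where an outside compounding pharmacy fills the prescription, the dispensed number may have to be requested. Some containers will not come back, and discarded or late-used capsules will still count as taken. Adherence over all enrolled patients may look less favourable. No dose, visit or treatment changes.
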